12.3 Common Serious Adverse Events

The following is a list of serious adverse events that the Sponsor considers to be associated with the disease state being studied. The list does NOT change your reporting obligations or prevent the need to report an adverse event meeting the definition of an SAE as detailed in Section 5.5.3 Definition of Serious Adverse Events (SAEs). The purpose of this list is to alert you that some events reported as SAEs may not require expedited reporting to the regulatory authorities based on the classification of "common serious adverse events". You are required to follow the requirements detailed in Section 5.5.7 Reporting of Serious Adverse Events (SAEs).

For IND safety reporting, single occurrences of the following events may be excluded from expedited reporting to the FDA. If aggregate analysis of these events indicate they occur more frequently with study drug, an expedited IND safety report may be submitted to the FDA.

- Anemia
- Anorexia
- Asthenia / Fatigue
- Back pain
- Bone pain
- Catheter related infection
- Dyspnea
- Haematuria
- Hydronephrosis
- Metastases to bone
- Metastases to central nervous system
- Nausea
- Obstructive uropathy
- Pain
- Prostate cancer metastatic
- Renal failure
- Renal failure acute
- Spinal compression fracture
- Spinal cord compression
- Urinary retention
- Urinary tract infection
- Urinary tract obstruction
- Vomiting

- CONFIDENTIAL -

7.5.6	Other Safety-Related Observations	25
7.6	Analysis of PK	25
7.7	Analysis of PD	25
7.8	Subgroups of Interest	25
7.9	Other Analyses	25
7.10	Interim Analysis (and Early Discontinuation of the Clinical Study)	25
7.11	Handling of Missing Data, Outliers, Visit Windows, and Other Information	25
7.11.1	Missing Data	26
7.11.2	Outliers	26
7.11.3	Visit Windows	26
8	DOCUMENT REVISION HISTORY	26
9	REFERENCES	27
10	APPENDICES	28
10.1	Appendix 1: Key Contributors and Approvers	28

I. LIST OF ABBREVIATIONS AND KEY TERMS

List of Abbreviations

Abbreviations	Description of abbreviations
IEC	Independent Ethics Committee
IGF	Insulin-like Growth Factor 1
IL6	Interleukin 6
IL8	Interleukin 8
INR	International Normalized Ratio
IRB	Institutional Review Board
ISN	International Study Number
JAK/STAT	Janus Kinase / Signal Transducer and Activator of Transcription
LA-CRF	Liver Abnormality Case Report Form
LBD	Ligand Binding Domain
LDH	Lactate Dehydrogenase
LFT	Liver Function Tests
LVEF	Left Ventricular Ejection Fraction
mCRPC	Metastatic Castration- Resistant Prostate Cancer
MedDRA	Medical Dictionary for Regulatory Activities
mg/dL	Milligram/Deciliter
mmHg	Millimeters of Mercury
mmol/L	Millimoles/Liter
MOA	Mechanism of Action
MRI	Magnetic Resonance Imaging
mTOR	Mammalian Target of Rapamycin
MUGA	Multiple Gated Acquisition
NASH	Non-alcoholic Steatohepatitis
NCI-CTCAE	National Cancer Institute - Common Terminology Criteria for Adverse Events
Ng	Nanogram
nmol/L	Nanomole/Liter
NYHA	New York Heart Association
OS	Overall Survival
PCWG2	Prostate Cancer Clinical Trials Working Group
PGAS	Pharmacogenomic Analysis Set
PHI	Protected Health Information
PK	Pharmacokinetics
PSA	Prostate-Specific Antigen
RBC	Red Blood Cell
RECIST	Response Evaluation Criteria In Solid Tumors
rPFS	Radiographic Progression-Free Survival
SAE	Serious Adverse Event
SAF	Safety Analysis Set
SAP	Statistical Analysis Plan
SOP	Standard Operating Procedure
TBL	Total Bilirubin
TLF	Tables, Listings and Figures
STNF1	Soluble Tumor Necrosis Factor Receptor – 1
TNF-alpha	Tumor Necrosis Factor - Alpha

Abbreviations	Description of abbreviations
TMF	Trial Master File
µL	Microliter
ULN	Upper Limit of Normal
US	United States
WBC	White Blood Cell

List of Key Terms

Terms	Definition of terms
Baseline	Observed values/findings which are regarded observed starting point for comparison.
Enroll	To register or enter into a clinical trial. NOTE: Once a subject has been enrolled, the clinical trial protocol applies to the subject.
Intervention	The drug, therapy or process under investigation in a clinical study that is believed to have an effect on outcomes of interest in a study. (e.g., health-related quality of life, efficacy, safety, pharmacoeconomics).
Investigational period	Period of time where major interests of protocol objectives are observed, and where the test drug or comparative drug (sometimes without randomization) is usually given to a subject, and continues until the last assessment after completing administration of the test drug or comparative drug.
Post investigational period	Period of time after the last assessment of the protocol. Follow-up observations for sustained adverse events and/or survival are done in this period.
Screening period	Period of time before entering the investigational period, usually from the time of starting a subject signing consent until just before the test drug or comparative drug (sometimes without randomization) is given to a subject.
Randomization	The process of assigning trial subjects to treatment or control groups using an element of chance to determine assignments in order to reduce bias.
Screening	A process of active consideration of potential subjects for enrollment in a trial.
Screen failure	Potential subject who did not meet one or more criteria required for participation in a trial.
Study period	Period of time from the first site initiation date to the last site completing the study.
Variable	Any quantity that varies; any attribute, phenomenon or event that can have different qualitative or quantitative values.

1 INTRODUCTION

This Statistical Analysis Plan (SAP) contains a more technical and detailed elaboration of the principal features of the analysis described in the protocol for study 9785-MA-1008, and includes detailed procedures for executing the statistical analysis of the primary and secondary endpoints and other data.

The SAP is finalized and signed prior to database hard lock, or accumulation of substantial amount of data in an open-label study to ensure lack of bias. If needed, revisions to the approved SAP may be made prior to database hard lock. Revisions will be version controlled.

This statistical analysis is coordinated by the responsible biostatistician of APGD-US. Any changes from the analyses planned in the SAP will be justified in the Clinical Study Report (CSR).

Prior to database hard lock, a final review of data and TLFs meeting will be held to allow a review of the clinical trial data and to verify the data that will be used for analysis set classification. If required, consequences for the statistical analysis will be discussed and documented. A meeting to determine analysis set classifications may also be held prior to database hard lock.

2 FLOW CHART AND VISIT SCHEDULE

Study Day	Screening Visit	1	29	57	85	113	141	169	Safety F/U	Unscheduled Visit ^a	Long-term F/U
Week	-4 to -1 (28 days)	1	5	9	13	17	21	25 and every subsequent 12 weeks	30 days after last dose^b	n/a	Every 12 weeks
Window (days)			± 3	± 3	± 3	± 3	± 3	± 3	± 7	n/a	± 7
Informed Consent	X										
Medical History	X										
Inclusion/Exclusion Criteria	X	X									
Vital Signs ^c	X	X ^c	X ^c	X ^c	X	X	X	X	X	X	
Physical Examination, Weight ^d	X ^e	X	X	X	X	X	X	X	X	X	
12-Lead ECG	X										
MUGA/Echocardiogram ^f	X										
Clinical Labs ^g	X	X ^h			X			X	X	X	
PSA ⁱ	X	X	X	X	X	X	X	X	X		
CT/MRI and Bone Scan ^j	X			X		X		X			
CXR or Chest CT	X										
ECOG PS	X	X			X			X	X	X	
Adverse Events ^k	X	X	X	X	X	X	X	X	X	X	
Concomitant Medications	X	X	X	X	X	X	X	X	X	X	
Study Drug Dispensing		X	X	X	X	X	X	X			
Long-Term F/U Assessments ^l											X
Study Drug Treatment ^m		X	X	X	X	X	X	X			
Blood Samples for CTCs and molecular profiling ⁿ	X				X						
Serum Samples ⁿ	X				X						

a Unscheduled visits may be performed at any time during the study whenever necessary to assess for or follow-up on adverse events, at the patient's request or if deemed necessary by the investigator.

b Or before the initiation of another systemic antineoplastic therapy, whichever comes first. AE and clinical lab assessment will be performed on the safety follow-up visit, regardless of initiation of another antineoplastic therapy prior to last dose of enzalutamide.

c Vital signs (blood pressure, heart rate, temperature) are to be obtained prior to, and 1–2 hours after the administration of study drug for the first 3 visits.

d A brief physical examination is required at each study visit, with the exception of the Screening visit during which a complete physical examination will be completed.

e Collect weight at this visit only.

f A MUGA scan or echocardiogram is required if the patient has a history of anthracycline treatment, or if the subject has congestive heart failure New York Heart Association (NYHA) class 3 or 4.

- g Laboratory assessments include serum chemistries and hematology.
- h Collect a blood sample for additional safety testing if indicated.
- i PSA progression, defined as a $\geq 25\%$ increase and an absolute increase of $\geq 2 \mu\text{g/L}$ (2 ng/mL) above the nadir, needs to be confirmed by a second consecutive value obtained 3 or more weeks later.
- j The window for all radiological assessments is ± 7 days. At Weeks 9, 17, 25 and subsequent assessments prior to treatment discontinuation, all other procedures must be completed within the ± 3 day window. Bone progression at the first reassessment at Week 9 requires a confirmatory scan 6 or more weeks later.
- k Adverse events, serious or non-serious, will be collected from the time the patient signs the consent form until the Safety Follow-Up visit, regardless of initiation of another anti-neoplastic therapy prior to last dose of enzalutamide.
- l Long-term follow-up for radiographic progressions (until progression or initiation of new anti-neoplastic therapy), survival, and subsequent anticancer therapies should be performed every 12 weeks for a maximum of 3 years from first dose. The study will end when the last subject has been followed for 1 year from date of first dose.
- m Enzalutamide will be administered until the disease progression, including radiographic progression or unequivocal clinical progression. Per the Investigator's clinical judgment and with sponsor approval, patients may be allowed to continue enzalutamide until the next treatment is initiated. If another non-cytotoxic, non-investigational, antineoplastic agent is initiated after protocol-defined progression has been determined, enzalutamide may be continued per the Investigator's clinical judgment and with sponsor approval as long as the patient is tolerating enzalutamide and continues androgen deprivation therapy
- n Blood samples for CTC molecular profiling and serum samples will be collected at baseline, week 13, time of PSA progression, and time of radiographic progression.

3 STUDY OBJECTIVE(S) AND DESIGN

3.1 Study Objective(s)

3.1.1 Primary Objectives

The primary objective is to determine radiographic progression-free survival (rPFS) of re-treatment with enzalutamide + GnRH analogue

3.1.2 Secondary Objectives

The secondary objectives are:

- Assess additional measures of efficacy:
 - Overall survival rate at 1 year
 - Time to PSA progression
 - PSA response rate [maximum decline of $\geq 30\%$, $\geq 50\%$, and $\geq 90\%$ from baseline, (PSA30, PSA50, and PSA90), respectively]
 - Objective response rate
- Time to first use of a subsequent antineoplastic therapy
- Assess safety of enzalutamide re-treatment in the post-chemo setting
- Assess correlative science in the post-chemo setting

3.2 Study Design

This is a US-based, multicenter, open-label, single-arm, study evaluating the efficacy, safety, and tolerability of open-label enzalutamide in the re-treatment setting. A total of 40 patients will be enrolled. Patients must have been previously treated with enzalutamide in the pre-chemotherapy setting for a minimum of 8 months, followed by docetaxel for a minimum of 6 cycles. Exposure to intervening systemic anti-cancer therapies such as abiraterone prior to docetaxel is allowed. Subjects will receive treatment with open-label enzalutamide (160 mg daily), administered as four 40 mg capsules, by mouth, once daily, until radiographic or clinical progression (such as pathological fracture, cord compression, worsened pain requiring radiation therapy, or opioid analgesic dose increase or initiation), or unacceptable toxicity. Per the Investigator's clinical judgment and with sponsor approval, patients may be allowed to continue enzalutamide until the next treatment is initiated. If another non-cytotoxic, non-investigational, antineoplastic agent is initiated after protocol-defined progression has been determined, enzalutamide may be continued per the Investigator's clinical judgment and with sponsor approval as long as the patient is tolerating enzalutamide and continues androgen deprivation therapy.

The consensus guidelines of the Response Evaluation Criteria in Solid Tumors (RECIST) 1.1 and the Prostate Cancer Clinical Trials Working Group 2 (PCWG2) will be utilized to determine radiographic disease progression. Radiographic disease progression is defined by RECIST 1.1 for soft tissue disease. Bone disease progression is considered when a minimum of two new lesions are observed. Progression on bone scan at time points prior to or at week 9 requires a confirmatory scan performed six or more weeks later. This confirmatory

scan should demonstrate at least 2 additional new lesions compared to the Week 9 scan (PCWG2).

The following assessments of prostate cancer status will be collected during the course of the trial: soft tissue disease on computed tomography (CT) scan or on magnetic resonance imaging (MRI), bone disease on radionuclide bone scans, and PSA.

Throughout the study safety and tolerability will be assessed by the recording of adverse events, monitoring of vital signs, physical examinations, and safety laboratory evaluations.

Subjects will have a safety follow-up visit approximately 30 days following the last dose of study drug or prior to the initiation of a subsequent anti-cancer drug or investigational agent, whichever occurs first. Survival will be followed every 12 weeks for a maximum of 3 years from first dose. The study will end when the last subject has been followed for 1 year from date of first dose.

Further details of the efficacy assessments can be found in the following sections of the protocol:

- 1) CT/MRI (imaging) Section 5.3.1
- 2) PSA Section 5.3.2
- 3) Correlative samples (biomarker) Section 5.3.3
- 4) Survival follow-up Section 5.3.4

3.3 Randomization

Not applicable to this study.

4 SAMPLE SIZE

Prior clinical trials data in the post-chemo setting have shown the following median rPFS for subject randomized to initial placebo, placebo+prednisone, or mitoxantrone+prednisone therapy:

- AFFIRM: Placebo = 2.9 months
- COU-301: Placebo + Prednisone = 3.6 months
- TROPIC: Mitoxantrone + Prednisone = 1.4 months

With a sample size of 40 subjects and an assumed median rPFS of 4 months for the therapy defined in this single-arm study, approximately 34 events are expected over a 12-month accrual and 12-month minimum follow-up. Further assuming uniform accrual, 10% loss to follow-up, and an exponential distribution for the rPFS event times, the expected lower bound of the 90% confidence interval for the median is approximately 2.5 months based upon simulations.

5 ANALYSIS SETS

In accordance with International Conference on Harmonization (ICH) recommendations in guidelines E3 and E9, the following analysis sets will be used for the analyses.

Detailed criteria for analysis sets will be laid out in Classification Specifications (CS) and the allocation of subjects to analysis sets will be determined prior to database hard lock.

5.1 Full Analysis Set (FAS)

The full analysis set will consist of all subjects who are enrolled in this study, receive at least one dose of study drug, and have at least one post baseline evaluation. This will be the primary analysis set for efficacy analyses.

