7.2.1 Full Analysis Set (FAS)

The full analysis set will consist of all subjects who are enrolled, receive at least one dose of study drug, and have at least one post baseline evaluation. This will be the primary analysis set for efficacy analyses.

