7.4 Analysis of Efficacy

The primary efficacy analysis will be conducted on the FAS.

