7.4.1.3 Subgroup Analysis

The analysis described in Section 7.4.1.1 may be repeated in subsets defined by baseline characteristics such as prior treatment, prior response to enzalutamide, biomarkers, etc. In addition, multivariable analyses may be conducted using multivariable analyses. This analysis will be conducted using the FAS.

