5.3 Safety Analysis Set (SAF)

For the statistical summary of the safety data, the safety analysis set (SAF) will be used. The SAF consists of all subjects who took at least one dose of study medication.

The SAF will be used for summaries of demographic and baseline characteristics and all safety and tolerability related variables.

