5.4 Biomarker Analysis Set (BAS)

The Biomarker analysis set (BAS) consists of the subset of the FAS population for which biomarker data are available to facilitate derivation of at least one of the correlative biomarkers. The Total N used in summaries and analyses for each unique biomarker will be the number of subjects with data available for that unique biomarker.

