6.1 Efficacy Endpoints

6.1.1 Primary Efficacy Endpoint(s)

The primary efficacy endpoint is radiographic progression-free survival (rPFS), which is defined as time from first dose to the radiological progression event or death.

The radiological PFS event is either radiological disease progression defined by either soft tissue tumor progression defined by RECIST 1.1, or the bone progression defined by the Prostate Cancer Clinical Trials Working Group 2 (PCWG2). The bone progression per PCWG2 is defined as a minimum of two new lesions are observed. Progression on bone scan at time points prior to or at Week 9 requires a confirmatory scan performed six or more weeks later. This confirmatory scan should demonstrate at least 2 additional new lesions (PCWG2) compared to the week 9 scan.

rPFS will be censored in the following scenarios:

- If patient has neither PD nor death, the PFS will be censored at last radiological tumor assessment date.
- If patient had PD or Death occurred more 24 weeks (168 days) after previous tumor radiological assessment. The PFS will be censored at last radiological tumor assessment date.
- If patient does not have post baseline tumor assessment, nor death within 24 weeks (168) after first dose, the PFS will be censored at Day 1.
- If patient took any new anti-cancer therapy before any PD event, the PFS will be censored at the last radiological tumor assessment date prior to the date of new anti-cancer therapy.

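### The primary efficacy set requires a post-baseline evaluation, so a dosed patient who dies before having one can drop out of rPFS, OS and cPFS

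*SAP*

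**What the plan says.** **The set.** Protocol 7.2.1 and SAP 5.1 give the Full Analysis Set (FAS) the same three conditions: enrolment, a dose, and a post-baseline evaluation ("receive at least one dose of study drug, and have at least one post baseline evaluation"). Protocol 7.2.1 adds: "This will be the primary analysis set for efficacy analyses". Protocol 7.4 repeats it for the main result ("The primary efficacy analysis will be conducted on the FAS"), and Protocol 7.4.1.3 does so for the subgroup and multivariable analyses ("This analysis will be conducted using the FAS"). No other set is named for OS or cPFS.

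**The detail.** SAP 5 defers the specifics: "Detailed criteria for analysis sets will be laid out in Classification Specifications (CS". That document is not part of the protocol or SAP.

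**The endpoints.** SAP 6.1.1 runs rPFS from first dose to radiological progression or death. SAP 6.1.2 runs OS from first dose to death from any cause. SAP 6.1.4 counts death in cPFS. For a patient with no post-baseline tumor assessment, SAP 6.1.1 censors at the start only if there is also no early death: "nor death within 24 weeks (168) after first dose, the PFS will be censored at Day 1". A death within 168 days without a scan is therefore an event.

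**The other sets.** The Safety Analysis Set (SAF) in SAP 5.3 has no post-baseline condition: "The SAF consists of all subjects who took at least one dose of study medication". The Biomarker Analysis Set (BAS) in SAP 5.4 inherits the FAS condition, because it "consists of the subset of the FAS population for which biomarker data are available".

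**The concern.** Entry to the primary efficacy set depends on something that happens after time zero, and an early death can prevent it. The patients who may be missing are those with the worst outcomes, so the loss is not random. SAP 6.1.1 shows that the authors meant to count early deaths without a scan, but the FAS rule is applied first and can remove some of them.

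The main results are a median rPFS with a 90% confidence interval and a one-year survival rate, both from one arm. The sample-size sections set the assumed median of 4 months beside control-group medians from earlier trials. A selective exclusion here has no counterpart in a comparator and would not cancel. Because the BAS is drawn from the FAS, the biomarker models for rPFS, OS and cPFS would also omit these patients, even where a Week 1 sample exists.

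**Working it through.** **1. The plan's own figures.** Protocol 7.1 and SAP 4 give 40 subjects, median rPFS 4 months, exponential times, uniform 12-month accrual, 12-month minimum follow-up and 10% loss.
- Hazard: L = ln 2 / 4 = 0.1733 per month.
- Probability of no event by the end: (e^(−12L) − e^(−24L)) / (12L) = (0.1250 − 0.0156) / 2.079 = 0.0526.
- Expected events: 40 × 0.9 × (1 − 0.0526) = 34.1, matching the stated 34.
- Simulation of 4,000 trials per loss pattern gives a mean lower 90% limit of 2.6 to 2.7 months, consistent with the stated value of about 2.5.

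The planning figures hold, and the point below does not alter them.

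**2. How many patients could be lost.** The documents give no count. The FAS rule makes most sense if any post-baseline visit is an evaluation: SAP 6.1.1 and 6.1.2 have rules for FAS patients without a scan or without a PSA, and these would have little use if the FAS required one. The patients at risk are then those who die before the Day 29 visit with no unscheduled visit. Day 29 is 28 days after Day 1, or 28 / 30.44 = 0.920 months. Protocol 1.2 gives median OS of 18.4 and 13.6 months for the two arms of the post-chemotherapy phase III enzalutamide trial. Assuming a constant hazard:
- Median 18.4: 40 × (1 − 0.5^(0.920/18.4)) = 1.4 deaths.
- Median 13.6: 40 × (1 − 0.5^(0.920/13.6)) = 1.8 deaths.

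This is an upper-end check, before allowing for the entry criteria and unscheduled visits. The range taken is d = 0, 1 or 2.

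**3. Effect on median rPFS.** Removing d early deaths from 40 rescales the later curve: S_FAS(t) = S(t) × 40/(40 − d). Setting this to 0.5 with a true exponential median of 4 gives

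median = 4 × [1 + log2(40/(40 − d))].

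| d | log2(40/(40 − d)) | Reported median (months) |
|---|---|---|
| 0 | 0 | 4.00 |
| 1 | 0.0365 | 4.15 |
| 2 | 0.0740 | 4.30 |

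A check at n = 40 with complete follow-up: the sample median is the midpoint of the 20th and 21st times. It becomes the 21st time after one early removal, and the midpoint of the 21st and 22nd after two. The mean gaps are (4/ln 2)/20 = 0.289 and (4/ln 2)/19 = 0.304. The shifts are 0.289/2 = 0.14 and 0.289/2 + 0.304/2 = 0.30, in agreement with the table.

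The planned distance from the median to its lower limit is 4.0 − 2.5 = 1.5 months, so the largest shift is 0.30/1.5 = 20% of it.

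**4. Effect on one-year OS.** Assume 20 of 40 are alive at one year (50%). One lost death gives 20/39 = 51.3%, and two give 20/38 = 52.6%. Whatever the true rate, the multiplier is 40/39 = 1.026 or 40/38 = 1.053.

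**The case against.** **Few patients, if any.** Entry requires a life expectancy of at least 6 months and ECOG 0–2 (Protocol 3.2), and a Safety Follow-up visit is planned after discontinuation unless consent is withdrawn (Protocol 6.1). A patient with a Week 5 or unscheduled visit who dies before the first scan is in the FAS under the broad reading, and SAP 6.1.1 counts that death. This stands, and is why the range stops at 2. It does not help a patient who dies before any visit.

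**The Classification Specifications may settle it.** They may define *evaluation*, and so narrow the number. The post-baseline condition itself is fixed in the protocol and SAP, so they cannot remove it.

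**The gap would be visible.** SAP 7.2.1 reports the size of each analysis set and SAP 7.5.1 the number of deaths. That discloses a gap without correcting the estimates.

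**Stronger readings that the documents do not support:**
- *Early deaths are certainly lost.* The text supports only that they can be, because the key term is undefined.
- *An evaluation means a tumor assessment*, so that deaths up to the Week 9 scan would be lost. The rule in SAP 6.1.1 for patients without a scan would then never apply within the FAS.
- *Living patients are dropped too, which would lower OS.* The schedules in both documents list long-term follow-up assessments every 12 weeks, and on the broad reading such a contact may be an evaluation. This loss is not established.
- *The PSA response denominator shares the defect.* Protocol 7.4.2 openly prespecifies patients with a post-baseline PSA. That is a separate rule, and a different choice there would be a preference.

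**Conclusion.** The concern holds in a limited form. The primary efficacy set can exclude a dosed patient whose early death is an event under the SAP's own definitions of rPFS, OS and cPFS, and any such exclusion biases the results upward.

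The size is small: at most about 0.3 months on a median of 4.0, and at most about 2.6 percentage points on a one-year OS of 50%. It is zero if no such patient occurs. These figures assume 0 to 2 lost deaths of 40, exponential rPFS and, for OS, 20 of 40 alive at one year. The analysis is descriptive, without a test or success threshold, so no formal decision changes. It should still be corrected, because the better set already exists and an undefined criterion for the primary set would otherwise be settled shortly before lock in an open-label study. Confidence is medium, since the Classification Specifications were not available.

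**What to change.** - **Primary set.** Analyse rPFS, OS and cPFS on all subjects who took at least one dose (the SAF definition in SAP 5.3). Amend Protocol 7.2.1, 7.4 and 7.4.1.3 and SAP 5.1 together so that the two documents agree.
- **Sensitivity analysis.** Keep the present FAS for this purpose, and define *post-baseline evaluation* in the SAP text.
- **Biomarker set.** State in Protocol 7.2.4 and SAP 5.4 whether the BAS is drawn from the new set.
- **Baseline tables.** SAP 7.2.3 puts these on the FAS, while Protocol 7.3 and SAP 5.3 use the SAF. Align them with the new primary set.

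The cost is a coordinated wording amendment to several sections of both documents and one additional run of the time-to-event tables. No new data are needed, and the sample-size figures stay as they are. If early deaths of this kind occur, the reported estimates will be slightly lower than under the present rule.
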